2.8.7 Other safety evaluation

Shift from baseline in Tanner stage will be summarized by sex, treatment, visit and Part. Additionally, shift in menarche status from baseline will be summarized by visit and treatment group and Part. Mean and SD of age of the participants in each of category of shift table will be provided. Listing will be provided.

In cases where following a Tanner stage 5 the data of the next visit are missing, they will be imputed as Tanner stage 5 (as the protocol does not mandate to repeat the Tanner stage assessment once Tanner stage 5 has been reached). Similarly, menarche data will be imputed as yes if the previous assessment was yes for menarche and data are missing at the next visit.

2.10 Biomarkers

Analyses of PCSK9 and lipids/lipoproteins are discussed in Section 2.7. No additional biomarkers will be evaluated in this study.

2.12 Interim analysis

Interim safety analyses are planned for the monitoring of participants' safety and will be performed as determined by the DMC (see DMC charter). Interim safety analyses before the unblinding for the analysis of Part 1 of the study will be performed by an independent statistician/programmer who will not be involved in the trial conduct. The interim results will be reviewed by the independent DMC.

3 Sample size calculation

The sample size was calculated based on detecting a reduction of at least the inclusion group compared to the placebo group in percent change of LDL-C from baseline to day 330. The primary efficacy variable is assumed to have a standard deviation of the control group and the inclusion group. These assumptions are based on observed results from adult inclusion studies.

The sample size of at least total participants will provide more than power to detect a reduction at significance level of randomization ratio.

Furthermore, in the adult HeFH inclision study (ORION-9), a SD of the in the control group and the inclision group was observed. With a more conservative assumption of a SD of the inclision group and the inclision group, the sample size of at least total

Novartis		Confide	ential	Page 39 of	48
Clinical Study Report Appendix 16		6.1.9, v1.0		Study No. CKJX839C123	01
	Novartis SAP amendment 4	For business	use only	Page 38 CKJX839C12301	
	participants will still pro significance level of	vide more than power	er to detect a	with a	
	The revised sample size r isparticipants.	requires a minimum of	articipants; how	ever, the actual enrollment	

4 Change to protocol specified analyses

5 Appendix

5.1 Imputation rules

5.1.1 Study drug

Missing/partial start date or end date of treatment will not be imputed.

5.1.2 AE date imputation

Partial AE start and end dates will be imputed. If there is uncertainty whether an AE occurred on-treatment or not, imputation will be performed, such that AE will be considered as on-treatment. Rules for imputing AE end date or start date will be provided in Programming Dataset Specification (PDS) document in details.

5.1.3 Concomitant medication date imputation

Rules for imputing the CM end date or start date will be provided in Programming Dataset Specification (PDS) document in details.

5.2 AEs coding/grading

The MedDRA version which will be available at the time of database lock, will be used for the coding purpose of the adverse events.

Novartis	For business use only	Page 39
SAP amendment 4	-	CKJX839C12301

5.3 Analyses to be performed in Part 1 analysis (ANA1) and Part 2 analysis (ANA2)

	Data to be included			Comment
	(ANA	Al and A	NA2 analysis)	
	Part 1	Part 2	Part 1 & Part 2 combined	
Disposition	ANA1	ANA2		
Protocol Deviations	ANA1	ANA2		
Demography and baseline characteristics	ANA1			
Concomitant therapies (Including lipid modifying therapy	ANA1	ANA2		SAF for ANA1; OAS for ANA2. CM will be counted in both parts when starting from part 1 and continuing to part 2.
New or changed lipid- modifying therapy	ANA1	ANA2		
Doses, Duration on study, Exposure	ANA1	ANA2	For exposure	
Efficacy (Primary & key secondary endpoints)	ANA1			
Efficacy (other Secondary endpoints)	ANA1	ANA2	For selected efficacy parameters	
AEs	ANA1	ANA2		SAF for ANA1; OAS forANA2
Diabetes assessment	ANA1	ANA2		SAF for ANA1; OAS for ANA2
Lab and Vital signs	ANA1	ANA2		SAF for ANA1;

Novartis	Confidential	Page 41 of 48	
Clinical Study Report Appendix 16.1.9, v1.0		Study No. CKJX839C123	
Novartis	For husiness use only	Page 40	
SAP amendment 4	For business use only	CKJX839C12301	

OAS for ANA2

5.4 Search criteria for AE of other safety topics

The most recent eCRS available during database lock will be used.

Novartis	For business use only	Page 41
SAP amendment 4		CKJX839C12301

5.5 Laboratory parameters derivations

The following table shows the criteria for clinically notable laboratory values. Not all parameters have notable criteria defined:

Table 5-1 Clinical notable criteria for selected laboratory tests

	Notable post-baseline value
Hematology	
Hemoglobin	$\leq 10 \text{ g/dL}$
Hematocrit	$\leq 0.8 \text{ x LLN}$
WBC count / Leukocytes	$\leq 2.8 \text{ x } 10^9/\text{L} \text{ or } \geq 16 \text{ x } 10^9/\text{L}$
Platelet count	$\leq 75 \text{ x } 10^9/L \text{ or } \geq 700 \text{ x } 10^9/L$
Clinical chemistry	
C(P)K	>5 x ULN
	>5 and $\leq 10 \text{ x ULN}$
	>10 and ≤20 x ULN
	>20 x ULN
Creatinine	\geq 50% increase from baseline (not >2 mg/dL)
	>2 mg/dL
	\geq 50% increase from baseline or >2 mg/dL
eGFR	<30 mL/min/1.73m2
	\geq 30 to <60 mL/min/1.73m2
	≥ 60 to <90 mL/min/1.73m2
Glucose	≥100 to <126 mg/dL
	≥126 mg/dL
HbA1C	≥5.7% to <6.5%
	≥6.5%

Novartis	For business use only	Page 42
SAP amendment 4		CKJX839C12301

Table 5-2	Notable liver function to	est values
		col valueo

Criterion
ALT > 3 x the upper limit of normal range (ULN)
ALT > 5 x ULN
ALT > 8 x ULN
ALT > 10 x ULN
ALT > 20 x ULN
AST > 3 x ULN
AST > 5 x ULN
AST > 8 x ULN
AST > 10 x ULN
AST > 20 x ULN
ALT or AST > 3 x ULN
ALT or AST > 5 x ULN
ALT or AST > 8 x ULN
ALT or AST > 10 x ULN
ALT or AST > 20 x ULN
Total bilirubin > 2 x ULN
TBL >2xULN & DBL >ULN
TBL >2xULN & DBL >2xULN
ALP > 2 x ULN
ALT or AST > $3 \times ULN$ and total bilirubin > $2 \times ULN$
ALT or AST > 5 x ULN and total bilirubin > 2 x ULN
ALT or AST > 8 x ULN and total bilirubin > 2 x ULN
ALT or AST > 10 x ULN and total bilirubin > 2 x ULN
ALT or AST > 20 x ULN and total bilirubin > 2 x ULN
ALT or AST > 3 x ULN and Total Bilirubin > 2 x ULN and ALP < 2 x ULN (Hy's law)

ALT = alanine aminotransferase, AST = aspartate aminotransferase, ALP = alkaline phosphatase, DBL = Direct bilirubin

When a criterion contains multiple laboratory parameters, the criterion will only be considered to have been met when all conditions occur within a 3-day window.

Novartis	For business use only	Page 43
SAP amendment 4		CKJX839C12301

5.6 Vital signs – definition of clinically notable values

The following table shows the clinical notable criteria for vital signs.

Table 5-3	Clinical I	notable	criteria	for vital	signs
-----------	------------	---------	----------	-----------	-------

Age	SBP [mmHg]	DBP [mmHg]	Heart Rate [beats min-1]
>=12 years	< 90, > 145	< 55, > 90	< 45, > 95

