5.1 Inclusion criteria

Participants eligible for inclusion in this study must meet **all** of the following criteria:

- 1. Written informed consent must be obtained from the participant's parent(s)/legal representative(s) prior to the adolescent's participation in the study. A consent or assent may also be required for some participants depending on their age and local requirements. *An informed consent must be obtained from participants once they reach the local legal age of adulthood during the study.*
- 2. Male or female participants, ≥ 12 to < 18 years of age at screening
- 3. HeFH diagnosed either by genetic testing or on phenotypic criteria according to the European Atherosclerosis Society Consensus Panel (i.e. elevated LDL-C plus a family history of elevated LDL-C, premature coronary artery disease and/or genetic diagnosis); see Section 16.1 (Appendix 1) for details of the criteria including LDL-C cutoffs
- 4. Fasting LDL-C >130 mg/dL (3.4 mmol/L) at the screening visit, measured at the central laboratory
- 5. Fasting triglycerides <400 mg/dL (4.5 mmol/L) at the screening visit, measured at the central laboratory
- 6. On maximally tolerated dose of statin (investigator's discretion) with or without other lipidlowering therapy (e.g. ezetimibe). Maximum tolerated dose of statin is defined as the maximum dose of statin that, at the investigator's discretion, can be taken on a regular basis without AEs that would lead to a reduction in statin dose
- 7. Participants on lipid-lowering therapies (such as statin and/or e.g. ezetimibe) should be on a stable dose for \geq 30 days before screening with no planned medication or dose changes during study participation
- 8. Participants on a documented regimen of LDL-apheresis will be allowed to continue the apheresis during the study, if needed. The apheresis schedule is not allowed to change during the double-blind period of the trial and must permit that an apheresis coincides with each study visit

- 9. Estimated glomerular filtration rate (eGFR) >30 mL/min/1.73 m² at screening
- 10. Willing to follow all study procedures including adherence to study visits, fasting blood draws, and compliance with study treatment regimens

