Vital signs	signs Vital signs include blood pressure and pulse measurements. After the participant has sitting for five minutes, with back supported and both feet placed on the floor, systolic blood pressure (SBP) and diastolic blood pressure (DBP) will be measured three time using an automated validated device, e.g. OMRON, with an appropriately sized cuff. repeat sitting measurements will be made at 1 - 2 minute intervals and the mean of the three measurements will be used. In case the cuff sizes available are not large enoug the participant's arm circumference, a sphygmomanometer with an appropriately sized may be used.	
	Clinically notable vital signs are defined in Section 16.2 (Appendix 2).	
Height and weight	Height in centimeters (cm) and body weight (to the nearest 0.1 kilogram (kg) in indoor clothing, but without shoes) will be measured. Height should be taken using a calibrated stadiometer.	

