16.2 Appendix 2: Clinically notable laboratory values and vital signs

Criteria for clinically notable vital signs are defined in Table 16-1:

Age	SBP [mmHg]	DBP [mmHg]	Heart Rate [beats min ⁻¹]
12 years*	< 90, > 130	< 50, > 80	< 50, > 105
>12 years	< 90, > 145	< 55, > 90	< 45, > 95
* criteria for 6-12 years			

Criteria for clinically notable laboratory values are defined in Table 16-2:

Table 16-2 Clinically notable laboratory abnormalities for selected tests		
Parameter	Alert Value	
Hematology		
RBC count	>50% increase, >30% decrease	
Hemoglobin	>50% increase, >30% decrease or any value <70 g/L (<7 g/dL)	
Hematocrit	>50% increase, >30% decrease	
WBC count	>50% increase, >50% decrease	
Platelet count	>75% increase, >50% decrease	
Clinical chemistry		
Albumin	<20 g/L (<2 g/dL)	
ALT	>150% increase	
AST	>150% increase	
Bilirubin (Total)	>100% increase	
BUN	>50% increase	
Calcium	>10% increase, >10% decrease	
C(P)K	>300% increase	
Creatinine	>50% increase	
Chloride	>10% increase, >10% decrease	
eGFR	>30% decrease	
Glucose	>50% increase, >50% decrease, or any value <3.3 mmol/L (<60 mg/dL)	
Potassium	>20% increase, >20% decrease, or any value >5.3 mmol/L (>5.3 mEq/L)	
Sodium	>5% increase, or any value >150 mmol/L (>150 mEq/L)	
Uric acid	>50% increase	

Table 16-2 Clinically notable laboratory abnormalities for selected tests

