2.8.5 Vital signs

Absolute values and change from baseline will be summarized for vital sign parameters by visit, time point, treatment group and Part. For SBP and DBP, average of 3 readings will be used for analysis while all 3 readings will be provided in the listing. Baseline and change from baseline in height, weight, and BMI will be assessed with/without using age- and sex-adjusted z-scores and summarized by visit treatment group and Part.

The number and percentage of patients meeting clinically notable criteria at any time, considering all data collected after first dose of double-blind treatment, from scheduled, unscheduled, and premature discontinuation visits will be summarized by treatment group and Part. The worst post-baseline value in each part will be used for this analysis. Notable criteria are defined in Appendix 5.6. Clinically notable criteria will be met when both of the following occur:

- Post-baseline value meets the clinically notable criteria.
- Baseline value does not meet the clinically notable criteria.

The baseline value is the last value prior to and up to Day 1 of the double-blind treatment.

All vital signs data will be listed by treatment group, participant, and visit/time and if clinically notable criteria are met, abnormalities will be flagged.

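### SAP Table 5-3 drops the protocol's age-12 vital-sign limits and uses the over-12 limits from age 12, so notable values in 12-year-olds do not follow the protocol's definition

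*SAP*

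**What the plan says.** Protocol Section 16.2 (Appendix 2), Table 16-1, has two age rows. The first is "12 years* < 90, > 130 < 50, > 80 < 50, > 105", with a footnote that these are the "criteria for 6-12 years". The second is ">12 years < 90, > 145 < 55, > 90 < 45, > 95". In each row the order is systolic pressure (SBP), diastolic pressure (DBP), heart rate (HR). The protocol makes this appendix the definition (Table 8-2: "Clinically notable vital signs are defined in Section 16.2 (Appendix 2").

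SAP Section 5.6, Table 5-3, has a single row: ">=12 years < 90, > 145 < 55, > 90 < 45, > 95".

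SAP Section 2.8.5 uses Table 5-3 for a summary, by treatment group and part: "The number and percentage of patients meeting clinically notable criteria at any time". For that summary, "The worst post-baseline value in each part will be used for this analysis", and a participant counts only if the baseline value was not already notable. The same criteria set the flags in the vital signs listing.

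Age 12 is within the study population (Protocol Section 5.1): "Male or female participants, ≥ 12 to < 18 years of age at screening".

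**The concern.** The two documents give different definitions of the same term for one eligible age. The SAP's six numbers are those of the protocol's older row, and only the age label has moved, from over 12 to 12 and over. Programming that follows the SAP will therefore classify the youngest participants by limits that the protocol does not assign to them.

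Vital signs are part of the safety endpoint in Protocol Table 2-1. At stake is whether the notable-value table and listing flags mean what the protocol says they mean for 12-year-olds. The disagreement runs in both directions, so the SAP is neither uniformly stricter nor uniformly looser at that age.

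**Working it through.** No planned figure is involved. The check sets the limits side by side and follows them into SAP Section 2.8.5. It reads age in completed years, which neither table states.

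**Step 1. Limits** (SBP and DBP in mmHg, HR in beats/min; bands in whole numbers)

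| | Protocol, age 12 | Protocol, over 12 | SAP, 12 and over | At age 12, protocol only | At age 12, SAP only |
|---|---|---|---|---|---|
| SBP | <90, >130 | <90, >145 | <90, >145 | 131–145 | none |
| DBP | <50, >80 | <55, >90 | <55, >90 | 81–90 | 50–54 |
| HR | <50, >105 | <45, >95 | <45, >95 | 45–49 | 96–105 |

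The SAP row equals the protocol's over-12 row on all six limits. Above age 12 nothing differs. At age 12 both documents flag SBP <90 or >145, DBP <50 or >90, and HR <45 or >105. The SAP analyses the mean of three pressure readings, so the exact bands for averaged values are SBP >130 to ≤145 and DBP >80 to ≤90 (protocol only), and DBP ≥50 to <55 (SAP only).

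**Step 2. Baseline exclusion.** Two examples for a 12-year-old, with the age-12 row applied throughout on the protocol side:
- Baseline SBP 135. Under the protocol limits baseline is already notable, so a later 150 is not counted. Under the SAP limits baseline is not notable, so the later 150 is counted.
- Baseline HR 100. Under the protocol limits baseline is not notable, so a later 110 is counted. Under the SAP limits baseline is already notable, so the later 110 is not counted.

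**Step 3. How long it lasts, if age is taken at the reading.** The youngest possible participant has just turned 12 at screening.
- Day 450 is 449 days after Day 1. That is more than 366, so everyone is at least 13.
- On the nominal schedule (screening on Day -28), Day 360 falls 28 + 359 = 387 days after screening, so everyone should be 13 by then too. This relies on visit timing, so Day 450 is the safe statement.
- Day 330 falls 28 + 329 = 357 days after screening, so a participant can still be 12.

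The overlap also shrinks within Part 1. Take participants aged 12 at Day 1 and assume birthdays spread evenly over the year. The share still 12 on Day d is 1 − (d − 1)/365:
- Days 30, 90, 150, 270, 330 and 360: 0.921, 0.756, 0.592, 0.263, 0.099 and 0.016, which sum to 2.647.
- Adding the 4-hour reading on Day 1 (share 1): (1 + 2.647)/7 = 52% of post-baseline Part 1 readings.

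**Step 4. How many participants.** SAP Section 1.1 gives 141 enrolled and a planned minimum of 40 in each age stratum. If those minima were met, the stratum from 12 to under 15 holds 40 to 141 − 40 = 101 participants. The number aged 12 could then be anything from 0 to 101. An even spread over six years of age would give 141/6 = 23.5, but the documents do not support that assumption or any other.

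**The case against.** The SAP may set its own reporting criteria, and it does so elsewhere. For hemoglobin, SAP Table 5-1 uses a value of 10 g/dL or below, where protocol Table 16-2 uses a relative change or a value below 7 g/dL. The age label was rewritten, which suggests intent. The SAP change history and its Section 4 on changes to protocol-specified analyses show no text in the public copy, so a documented decision cannot be excluded. The count of notable vital signs is itself a SAP addition: Protocol Section 12.5.2 asks only for summary statistics, with flags in the listing. A single row also avoids changing limits on a birthday. All of this stands, and it means the change cannot be called an unexplained mistake. It does not remove the conflict, because two current tables still define one term differently for 12-year-olds.

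The consequence is also modest. The same limits apply to both arms, absolute values and changes are summarised by visit, every reading is listed, and no efficacy test is touched. That stands in full.

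A reader might infer three stronger things:
- That raised blood pressure in 12-year-olds goes unflagged. It does so only within SBP 131–145 and DBP 81–90; higher readings are flagged by both documents.
- That the SAP wrongly flags ordinary heart rates. The documents show only that HR 96–105 is not notable at age 12 under the protocol. Whether such rates are ordinary, and which limit is right, are clinical judgements that the documents do not make.
- That a definite share of participants is misclassified. A simulation could produce one, but only from assumed means and standard deviations that are in neither document. Holding age at 12 for every later reading would also overstate it, since about half of those readings fall after the 13th birthday (Step 3).

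**Conclusion.** The point holds as a contradiction between the two documents. For a participant aged 12, the SAP departs from the protocol's own definition in five bands: SBP 131–145, DBP 81–90 and HR 45–49 are not flagged, while DBP 50–54 and HR 96–105 are. The effect reaches the notable-value counts, the baseline exclusion and the listing flags, and nothing else. If age is taken at the reading, it has ended by Day 450.

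The effect on counts cannot be computed, because neither the number of 12-year-olds nor their vital-sign values are given. The conclusion assumes age in completed years. It is a safety-reporting inconsistency that should be corrected, and it does not threaten the primary result.

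**What to change.** Reconcile the two tables in one of two ways: carry both rows of protocol Table 16-1 into SAP Table 5-3, or align the protocol with the single SAP row and state the departure and its reason. Which limits to keep is for the sponsor's clinical team.

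If both rows are kept, add one sentence on age. It should apply the same row to a participant's baseline and post-baseline readings, for example the row for age at baseline. If the row instead switched at the 13th birthday, an unchanged HR of 100 or DBP of 52 would be not notable at 12 and newly notable at 13. Under an age-at-baseline rule, participants who were 12 at baseline stay on the age-12 row in Part 2 as well, so the SAP should say so.

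The cost is one table row, one sentence and one line of derivation code. No new data are needed. The front page of the SAP appendix already records an analysis added after the Part 1 database lock, so the Part 1 table and listing would be rerun and the change recorded as made after that lock.

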5.7 Statistical models

5.7.1 Multiple Imputation Wash-out model

A multiple imputation washout model will be utilized for the primary efficacy analysis of the percentage change in LDL-C from baseline to Day 330 endpoint. The washout model can be thought of as a modified control-based PMM that will be used to explore the possibility of missing data being MNAR for subjects who discontinued the study early. For subjects who discontinued the study early, their missing values will be imputed under the assumption that their outcome would be similar to those in the placebo group with similar background characteristics. For subjects in the inclisiran group only missing Day 330 values will be imputed. For subjects in the placebo group their missing values over all visits after early termination will be used to account for uncertainty in the imputation process and results from the imputed datasets will be combined using Rubin's method. Further details are provided below.

For the placebo group the following variables will be included in a multiple imputation procedure (SAS PROC MI), this assumes missing data are MAR:

- Baseline value of efficacy measurement (continuous)
- Observed value of efficacy measurement at Day 90 (continuous)
- Observed value of efficacy measurement at Day 150 (continuous)
- Observed value of efficacy measurement at Day 270 (continuous)
- Observed value of efficacy measurement at Day 330 (continuous)
- Observed value of efficacy measurement at Day 360 (continuous)

For the subjects in the inclisiran group who completed first 3 doses and have data available after Day 330 (considered to have completed the Study Part 1) the following variables_will be included in a multiple imputation procedure (SAS PROC MI), this assumes missing data are MAR:

- Baseline value of efficacy measurement (continuous)
- Observed value of efficacy measurement at Day 330 from the inclisiran group (continuous)

For the remaining subjects in the inclisiran group the following variables will be included in a multiple imputation procedure (SAS PROC MI), this assumes missing data are MNAR:

• Baseline value of efficacy measurement (continuous)

Novartis	Confidential	Page 45 of 48
Clinical Study Report Appendix 16.1.9, v1.0		Study No. CKJX839C12301

Novartis	For business use only	Page 44
SAP amendment 4		CKJX839C12301

• Observed value of efficacy measurement at Day 330 from the placebo group (continuous)

- 1. Intermittent missing data in the placebo treatment group will be imputed using Markov Chain Monte Carlo (MCMC) methods, assuming MAR. SAS PROC MI will be utilized for this step using the MCMC impute=monotone option. A total of 100 datasets will be created. These datasets will be utilized in Step #2.
- 2. The remaining missing values in the placebo group with a monotone missing data pattern will be imputed in this step. Missing data will be imputed assuming data are MAR. Only subjects in the placebo group will be utilized in this step. SAS PROC MI will be used to impute missing values utilizing the monotone reg option. Baseline age group will be included in the regression model. This will be performed for the 100 datasets. After this step, the 100 datasets will be fully imputed for the placebo treatment group. These datasets will be utilized in Step #4.
- 3. Subjects in the inclisiran group who received first 3 doses of study medication, have the Day 330 value missing, and have evaluable data after Day 330 will be included in this step. Missing values at Day 330 will be imputed assuming data are MAR. Only subjects in the inclisiran group will be included in this step. Observed Baseline data, Day 330 data and baseline age group will be utilized to impute missing Day 330 data utilizing SAS PROC MI. This will be performed 100 times to create 100 datasets that are fully imputed at Day 330.
- 4. The remaining missing values at Day 330 in the inclisiran group will be imputed in this step. Note that the subjects with imputed inclisiran Day 330 data from Step #3 will not be utilized in this step. Control-based PMM imputation will be performed. With this imputation model, the missing efficacy measurements in the inclisiran group will not be constructed from the observed data in the inclisiran group but rather from the observed and imputed data in the placebo group at Day 330. Baseline data and age group will also be utilized in the imputation. The MNAR statement in SAS PROC MI will be used to impute missing values. This will be performed for the 100 datasets.
- 5. The imputed data from Step #3 will be combined with the imputed data from Step #4 to create 100 fully imputed datasets.
- 6. A total of 100 fully imputed datasets will be created (M=100). Since multiple imputation is a stochastic method, slight differences in output can be expected for different initial states of the random number generator. The seed numbers will be identified in the SAS programs to allow for reproducibility.
- 7. After the missing data imputation is completed using the above steps, absolute change/percentage change values will be calculated in each of the imputed datasets at each visit.
- 8. These 100 datasets will be analyzed using ANCOVA models with fixed effects of treatment group: baseline age group and baseline LDL-C as a covariate for the percent change of LDL-C from baseline to Day 330 primary efficacy endpoint. PROC MIXED with (repeated / group=treatment) statement which allows separate variance to estimate for treatment groups will be used.

Novartis	For business use only	Page 45
SAP amendment 4		CKJX839C12301

9. Treatment effects (difference in least squares (LS) means between treatments) from these 100 analyses will then be combined using Rubin's Method via SAS PROC MIANALYZE procedure for each endpoint.

